including HbA1c, as well as lipid panels, CRP, IL-6, TNF-alpha, and free fatty acids (FFA). This will be followed by a 3-hour intravenous glucose tolerance test (IVGTT) which will begin at 8 AM and terminate at 11 AM. During the IVGTT, a dietitian will meet with each participant individually to ensure that they will follow a standard diet pattern during the 1 year-intervention (45% carbohydrate, 35% fat and 25% protein) to avoid any confounding effects on our measurements. All participants will be asked to maintain a **3 day food record** monitoring their energy intake during the course of the study. The diaries will be evaluated weekly by the dietitian to provide monthly feedback. All participants will meet with the dietitian three times during the study to ensure appropriate adherence to the diet pattern throughout the study. The vastus lateralis muscle will be biopsied to measure protein expression and to determine mitochondrial enzymatic activities.^{75, 76}

Twenty-four participants will be randomly assigned to either one year of TRT+LPWS (n = 12) or a TRT+ standard NMES (n = 12). Testosterone patches (Tp; 4

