-8 mg/d) will be re-placed daily on alternating skin sites at bedtime for 1 year. Randomization will be done at the end of the two-day assessment period using a random number generator computer program (baseline). Participants will be block randomized based on the degree of denervation (lower or higher than 50% of compound muscle action potential (CMAP) of the standard normal femoral nerve values). Both groups (TRT+LPWS & TRT+ standard NMES) will undergo 1 year of supervised unilateral progressive RT, twice weekly, using ankle weights. The two-day assessment period will be repeated using the same sequence at 6 months and after 1 year. Prior to training, we will perform multiple neurophysiological tests to confirm LMN denervation of the knee extensor muscle group. The first technique is to place the surface NMES electrodes on knee extensor muscle group and increase the current (30 Hz, 450 µs) gradually up to 200 mA. If the knee extensors show visible elicited contraction, then the participant will be disgualified from the study. If there is no response, participant will then be escorted to the EMG lab and further testing for evidence documenting muscle denervation will be performed by a trained electromyographer. Briefly, participants will undergo a femoral nerve motor conduction study with recording of the CMAP from the vastus medialis (VM) with supramaximal femoral nerve stimulation just below the inguinal ligament. The participant will undergo needle EMG of the vastus medialis to determine the presence and intensity of spontaneous muscle fiber fibrillation potentials to quantify the level of denervation. A monopolar EMG needle electrode will be inserted into the VM muscle to record spontaneous intramuscular activity in the resting muscle.

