Statistical Analyses. Means and standard deviations or frequencies and percentages will be reported for all data. Similar summaries will be provided for all outcome and biomarker data separately at baseline, 6-, and 12-months. A repeated-measures ANOVA will be used to analyze the primary study outcome, skeletal muscle size, with treatment, time, and the interaction of these variables included in the model. A first order autoregressive correlation structure will be used to capture the dependency within subjects' outcomes. A specific contrast will be used to determine if the change from baseline for the treatment group is different than that of the control group. A model selection procedure will be performed due to the relatively large number of predictor variables compared to the number of subjects for specific aims 2 and 3. A penalized random effect model will be used to suggest the important predictors for each outcome separately. These include each specific predictor mentioned in the specific aims as well as injury characteristics.⁸⁴ A parsimonious model will be chosen by the Bayesian information criterion. Since the aforementioned model is well-suited for model selection, but results in biased parameter estimates, an unpenalized random effects model will be fitted based on the parsimonious model and used for inference. Study period will be included in all analyses, and a time by group interaction will be included for the analyses associated with Specific Aim 3. All statistics will performed with R (3.3.0) with the 'glmmLasso' package. Prior to any statistical analysis, any of the biomarkers may be transformed to ensure all statistical assumptions are met. A simulation study was used to determine the power achieved from the proposed study if 5% of subjects were assumed to drop out at the 12-month observation point. One thousand datasets were created with Cohen's d varying between 0.5 and 2.0, with the anticipated 24 subjects being equally allocated to the treatment and control groups and the subjects' outcomes having a correlation of 0.25. A linear mixed-effects model was used to analyze the simulated data using a one-sided test at α =0.05. Results of the study show that this design will have the power to detect differences of d=1.28 with 80% power and d=1.48 with 90% power. An intent-totreat approach will be used to deal with missing data. If the missing data is due to drop-out, the statistical methods are valid as long as the data mechanism is considered missing at random or missing completely at random.

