The current interventions **may not be applicable** to those who have pain or intolerance to the stimulation parameters. **1**) Only those with LMN denervation may benefit the current protocol. **2**)

Although LMN injury may evenly spread across different segments of the cord, we are interested in studying the large knee extensors because of its established metabolic activities. **3)** Every effort will be made to recruit individuals with TSI less than 5 years to ensure appropriate response to LPWS; however, the study will include others who have been injured for more than 5 years to ensure generalization to those with long-term LMN denervation. **4)** The Grass S88X is intended for research use only and not for clinical applications. However, successful completion of this proposal will allow clinical translation and ensure safety of introducing these stimulation parameters to the clinical field. The unit does not require FDA approval to be used for human with SCI, it does only require IRB approval prior initiation of the trial.

Other Limitations and Alternatives: The current study is limited by

1) The fact that the effects of training and increased muscle mass may be influenced by increased dietary intake, which may confound the primary outcome measures. We will evaluate the caloric intake reports from our participants on a monthly basis. This will allow us to closely monitor extra-caloric intake and we will regularly instruct our participants if the caloric intake exceeds 300-500 Kcal/week of their pre-measured BMR.

2) Some individuals may complain of skin rashes when wearing the transdermal patches; glucocorticoid cream will be prescribed for use after each patch is removed and participant will be excluded if the problem is persistent.

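### Time since injury is tied by the protocol to LPWS response but is absent from the primary model, so a chance imbalance among 24 men can shift the estimated effect and costs precision

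*Combined protocol and SAP*

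**What the plan says.** Section 6 (Limitations and Alternatives) gives a reason for preferring recently injured men: "Every effort will be made to recruit individuals with TSI less than 5 years to ensure appropriate response to LPWS". It then adds that "the study will include others who have been injured for more than 5 years", for the sake of generalisation. The inclusion criteria in Section 4 set a minimum of one year since injury and no upper limit, so a mixed sample is planned.

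Randomisation is described in Section 4: "Participants will be block randomized based on the degree of denervation", with the cut at 50% of the normal femoral CMAP. No other factor is named. Allocation is 12 men per arm.

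In Statistical Analyses, the primary outcome is analysed by repeated-measures ANOVA of "skeletal muscle size, with treatment, time, and the interaction of these variables included in the model". The test is a contrast to "determine if the change from baseline for the treatment group is different than that of the control group". Predictor selection is described separately and is justified by the "relatively large number of predictor variables compared to the number of subjects for specific aims 2 and 3". Of the candidate predictors in those models it says: "These include each specific predictor mentioned in the specific aims as well as injury characteristics". No TSI-adjusted or TSI-subgroup analysis of muscle size is described.

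**The concern.** The protocol names one patient characteristic as bearing on response to the experimental stimulation, plans to enrol men on both sides of its 5-year mark, and then leaves that characteristic out of the primary analysis. The secondary aims can take up injury characteristics; the primary aim cannot.

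If response depends on TSI, the observed difference in a trial of 24 depends partly on which arm happens to receive more of the recently injured men. The change-from-baseline contrast removes any effect of TSI on starting muscle size, but not an effect on response. The preliminary data in Section 3 also report wide, unexplained variation in response to stimulation training. That is a reason to use the one explanatory factor the protocol does name. At stake are the size of the estimated effect in the trial as run, and some avoidable loss of precision.

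**Working it through.** **Inputs from the documents.** 24 men, 12 per arm; one-sided α = 0.05; correlation 0.25; 5% dropout at 12 months; stated power 80% at d = 1.28 and 90% at d = 1.48 (Section 4).

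**Assumptions.** The share of men under 5 years and the size of any TSI effect are not in the documents. Ranges are shown.

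**1. The plan's own power.** With the same correlation of 0.25 between all visits, the SD of change is √(2 × (1 − 0.25)) = 1.225 outcome SD. The standard error of the contrast is 1.225 × √(2/12) = 0.500.
- d = 1.28: 1.28/0.500 − 1.645 = 0.915, power 0.82 (0.80 with a t reference on 22 df).
- d = 1.48: 1.48/0.500 − 1.645 = 1.315, power 0.906 (0.89 with t).

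The stated figures are reproduced to within about 2 points.

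**2. Chance of imbalance.** If K of the 24 men are under 5 years, the number falling in the LPWS arm is hypergeometric: P(x) = C(K, x) × C(24 − K, 12 − x) / C(24, 12), where C(24, 12) = 2,704,156. For K = 12, a difference of 4 or more means 8:4 or worse in either direction: 2 × (495² + 220² + 66² + 12² + 1) / 2,704,156 = 595,852 / 2,704,156 = 0.22.

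| Men under 5 years, of 24 | P(arms differ by 4 or more) |
|---|---|
| 12 | 0.22 |
| 8 or 16 | 0.19 |
| 6 or 18 | 0.15 |
| 20 | 0.09 |

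Blocking within two equal denervation strata unrelated to TSI leaves this at 0.20 to 0.23 for K from 8 to 16.

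**3. Shift from an 8:4 split.** Shift = TSI effect × (8/12 − 4/12) if TSI acts in both arms. If TSI acts only under LPWS, the shift from the whole-sample effect is TSI effect × (8/12 − 6/12), which is half as much.

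| TSI effect on change (outcome SD) | Shift, both arms | Share of d = 1.28 | Shift, LPWS only |
|---|---|---|---|
| 0.5 | 0.17 | 13% | 0.08 |
| 1.0 | 0.33 | 26% | 0.17 |
| 1.5 | 0.50 | 39% | 0.25 |

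**4. What adjustment does.** Simulation with 10,000 trials per scenario: half the men under 5 years, TSI acting equally in both arms, SD of change held at 1.225, d = 1.28, 5% dropout.

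| Change variance explained by TSI | Power, unadjusted | Power, adjusted |
|---|---|---|
| 0% | 0.78 | 0.76 |
| 10% | 0.77 | 0.79 |
| 20% | 0.78 | 0.84 |
| 30% | 0.77 | 0.87 |

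At 20%, the TSI effect is √(0.20 × 1.5 / 0.25) = 1.10 SD. An 8:4 split should then move the estimate by 1.10/3 = 0.37. The simulated unadjusted means are 1.67 when the split favours LPWS and 0.90 when it goes against it. Power given the split is 0.96 or 0.52 unadjusted, against 0.81 to 0.83 adjusted. With no treatment effect, the rejection rate given the split is 0.15 or 0.01 unadjusted, against 0.04 to 0.05 adjusted. Over all splits, the unadjusted mean is 1.29 and the type I error 0.05.

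**5. If TSI acts only under LPWS.** Suppose recently injured LPWS men gain 25%, and all other men gain nothing. With 8:4, the unadjusted difference is 25 × 8/12 = 16.7 points; with 4:8 it is 25 × 4/12 = 8.3. Adding TSI weights the within-class differences (25 and 0) by 8 × 4/12 = 2.67 each. The result is 12.5 points for both splits, which is the whole-sample value.

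**The case against.** The strongest reply is that this is ordinary sampling variation. Allocation is random, so the estimate is unbiased over repeated trials and the overall type I error stays near 0.05. Unmodelled TSI variation also goes into the residual, so the reported interval allows for it. In the example of step 5 with a 6:6 split, the SD within the LPWS arm is about 13 points and the standard error of its mean about 3.8. The split alone contributes 25 × √(0.25/12 × 12/23) = 2.6 points. All of this stands. A reader might infer that the planned primary test is biased or invalid; it is not. What remains is the shift conditional on the split that occurs, and the lost precision.

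A reader might also infer that TSI decides who responds. Section 6 does not say that. It links TSI under 5 years to an appropriate response and gives no size, shape or evidence for a threshold. The all-or-none 25% example is an illustration without a source.

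Nor do the documents support a general false-positive claim. Section 4 expects the control current to produce no contraction, so an effect of TSI confined to LPWS is the reading closest to the text. In that case imbalance changes the size of a real effect but cannot create one. The conditional rejection rate of 0.15 needs TSI to affect change in both arms, for example through the response to testosterone, which the documents do not assert.

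Finally, Section 6 favours recruitment under 5 years, so the share may exceed half; 22% is then the upper end of the range.

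It may also be tempting to say that the CMAP cut separates few men and should give way to TSI. The documents contain no CMAP distribution, and Section 5 expects differing levels of denervation. Blocking on one factor in 24 men is defensible.

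**Conclusion.** The gap is real and specific to the primary analysis: the protocol links TSI to LPWS response, admits men on both sides of 5 years, and neither balances nor adjusts for TSI when testing muscle size. A difference of 4 or more recently injured men between arms has roughly a 1 in 5 chance when a third to two thirds of the sample are under 5 years, and less when recruitment succeeds in favouring them. For TSI effects of 0.5 to 1.5 SD, an 8:4 split moves the contrast by 0.17 to 0.50 SD if TSI acts in both arms, and by half that if it acts only under LPWS. These sizes rest on an assumed TSI mix and assumed TSI effects. The point concerns precision and the interpretation of a single small trial; it does not show that the planned test is invalid.

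**What to change.** Before unblinded data are seen, add TSI to the primary repeated-measures model, either as a continuous variable or as under 5 versus 5 or more years, together with TSI-by-time and the CMAP randomisation stratum. State the chosen form in advance. The TSI-by-time term is the one that matters: a TSI main effect alone moves all visits equally and does little to the change contrast. The CMAP stratum should enter in the same way.

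Keep the CMAP blocking as it is. A second blocking factor with 24 men would risk sparse blocks, and covariate adjustment does not need it.

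No new data are required, since the date of injury is already needed to establish eligibility. The cost for TSI is about 2 points of power (0.78 to 0.76) if it proves unrelated to change, against a gain to 0.84 if it explains 20% of change variance in both arms. For the same TSI effect confined to LPWS, the gain would be smaller; it was not calculated. Nor was the further small cost in degrees of freedom of the CMAP terms.

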- e) A portion of \$3000 subjects' reimbursement fee will be dedicated to reserve a room for non-veteran participants who may need lodging at Candlewood suites which is located 4.5 miles away from our center.

- f) For the TRT+ standard NMES (control group; n=12), we will provide the option to carry out the training at their home using our established videoconference telehealth system and monitor the training using a hand-held battery operated stimulator, which is pre-customized and ready to be used (see supplement). We have 5 Empi stimulators in our laboratory and do not need to buy any additional units. This will ensure subject retention at least in the control group and will allow the study team to focus on the retention of the other 12 participants in the TRT+LPWS group.
- g) Providing financial reimbursement, social interaction during training sessions and access to the data at the conclusion of the study are additional methods to be utilized to reduce subject attrition.
- h) [name] will work closely with each participant to resolve any scheduling barrier and will allow morning and evening schedules.
- i) We will also provide a comprehensive team approach that will allow our participants free consultations with dietitian, psychologist and participation in our recreational activity program.

Potential Risk	Potential effects of risk Po	otential seriousness
Anthropometrics	Bruising, discomfort	Occasionally
Venous catheter insertion and blood draws	Localized swelling, soreness, bruising, and chance of infection, bleeding, pain, lightheadedness or possible fainting. A total of 12 tablespoons will be collected.	d Occasionally
IV line failure	Discomfort, swelling, redness over the IV line site causing failure to use the line. Another IV will need to be placed in another part of the arm.	Occasionally
Insulin Sensitivity Tests	Hypoglycemia (low blood sugar) with occasional dizziness, sweating, and nausea, seizures, coma, or death	Occasionally Unlikely
Basic Metabolic Rate	Anxiety, apnea, and claustrophobia	Occasionally
Autonomic Dysreflexia	Slow heart rate, high blood pressure, headache flushing and sweating.	Unlikely
DXA	Fall during transfer This study will involve exposure to radiation from 3 whole body DXA scans and regional scans for hips and knees. This radiation exposure is not necessary for medical care and is for research purposes only. All radiation increases the risk of developing cancer in the future. The total amount of	al

7. Risk to Subjects

		· · · · · · · · · · · · · · · · · · ·
	radiation in this study is equal to less than one day of exposure from natural background radiation. The McGuire VA Medical Center Radiation Safety Committee will review the use of radiation in this research study and will approve the use as involving acceptable risk and necessary to obtain the research information desired. Physicians will be informed about the research to help their participants to make the correct decision.	
MRI	Anxiety, dizziness, and claustrophobia	Occasionally
Muscle Biopsy	Localized swelling, soreness, bruising, chance of infection, bleeding, pain, lightheadedness or possible fainting. The numbing medication can cause allergic reaction including local skin rash and rapid heart rate.	Uncommon
	 Light-headedness, shortness of breath and altered heart rate& blood pressure leading to autonomic dysreflexia. Muscle soreness at your neck, upper back, shoulders, arms & hands Fracture Autonomic dysreflexia (slow heart rate, high blood pressure, headache flushing & sweating) which may be life threatening Pressure Ulcers Fainting, heart attacks or death 	Unlikely
Testosterone Replacement Therapy	Serious reactions Severe rash at site of the patches, worsening heart failure that may cause difficulty for pumping blood, swelling of the body, enlarged prostate causing difficulty in urination, increase in red blood cells which may cause blood clots in the legs (cause swelling), chest pain, shortness of breath and rarely death and brain damage (causing a stroke), infertility, prostate cancer, difficulty in breathing during sleep, blood in urine. Common reactions	Occasionally occurs
	Application site reactions, back pain, enlarged prostate, headache, irritations of the skin,	

depression, enlarged breasts, increase cholesterol which may increase the risk of heart disease, chills, diarrhea, fatigue, frequent	
urination, pain during urination, reduced sex drive, inflammation of prostate, rash, acne, confusion	

a. Protection against Risk:

Every effort will be made by the PI and the study team to minimize potential risks. Any procedures will be carried out in accordance with any standard operating procedures and study staff will receive the necessary training to mitigate risks. There will be strict adherence to the inclusion & exclusion criteria of the protocol. Appropriate health screening and strict compliance with the established exclusion criteria will minimize attrition due to medically related causes. Subjects will be closely monitored by study personnel at all visits. All subjects will be provided with 24-hour contact information for the investigator and instructed to call for any concerns. Unscheduled visits may be performed if required for evaluation of safety. If a subject has an adverse event, more frequent visits may be necessary.

b. Adequacy of Protection from Risk:

Protection of skin integrity during Anthropometry:

Skin will be closely checked following each measurement to ensure no redness or scratches.

Protection from risk associated with transfers:

To minimize risk, an investigator will be available to assist in all transfers, and provide a slide board or any other assistive devices needed. Our labs are equipped with ceiling lifts that facilitate the transfer process from wheelchairs to any other station.

Protection against risk of autonomic dysreflexia (AD).

Our sample is limited to T10 and below, we have developed a protocol by carefully monitoring blood pressure and heart rate every 2-3 minutes in persons with SCI. Moreover, our training protocol provide us with an opportunity to space out time between NMES repetitions in persons who are susceptible of developing AD risk. This ensures the participants can safely continue the training and reduce the potential risk. Following 4-8 weeks of training, participants' free nerve endings become acclimatized to the electrical signals during NMES.

Protection from risk associated with Dual Energy X-ray Absorptiometry (DXA) Scan:

To minimize risk, only the required scans will be performed. An overhead lift system has been installed to ensure safe transfers on and off scanner. All study procedures have to be approved by our Radiation Safety committee prior obtaining IRB approval.

Protection from risk associated with MRI:

To minimize risks an MRI safety checklist will be used to ascertain it is safe for subjects to have an MRI. Only board certified radiologists at McGuire VAMC will be utilized.

Protection from risk associated with venous catheter insertion and blood draws:

To reduce risk, all blood drawing will be performed by certified personnel using aseptic techniques and universal precautions. All blood draws will be performed by well-trained certified nurses who are working in our SCI center. IVGTT dose calculation and test will be carried out and administered by a medical doctor and the participant will be under full medical supervision during the test.

Protection from risk associated with muscle biopsy:

The muscle biopsy will be conducted at the McGuire VA Medical Center. Three biopsy samples of the vastus lateralis muscle (25-50 mg wet wt.) will be obtained by a 14 gauge Tru-Cut needle by [name]. Biopsies will be obtained before the trial (baseline), mid-intervention (6 months) and after 1 year of completing the trial (post-intervention) using a sterile technique and local anesthesia (2% lidocaine). The skin overlying the muscles will be prepped and draped in a sterile fashion and 3cc 2% lidocaine will be locally administered. A 5 mm skin incision will then be made with a #10 scalpel. The biopsy samples will be obtained from one site incision, after which the site will be closed with Steristrips and an overlying sterile adhesive dressing. Furthermore, a pressure dressing will be administered for at least 10 minutes. Following the muscle biopsy, [name] will provide the participants with extra supplies in case the dressing needs to be changed. One of our SCI physicians will examine all the participants within 48 hours after conducting the muscle biopsy. This procedure has been successfully completed in our previous CDA2 trial (n=22) without a single adverse event reported.

Protection from risk associated with resistance training and LPWS neuromuscular electrical stimulation

[name] will review all DXA scans to determine that participants can safely exercise without risk of fracture. Participants with knee BMD less than 0.6 g/cm² and hip T-scores below -3.5 SD or previous bony fracture around the knee joint within the last 2 years will be excluded from the trial. [name] will supervise all aspects related to the protocol including proper ankle weight positioning, placement of the electrodes and monitoring vital signs during electrical stimulation.

Protection from risk associated with Testosterone (T) Replacement Therapy (TRT)

[name] will clinically and medically supervise all our participants during the course of the study. Possibility of skin rashes will be treated with glucocorticoid cream after removal of T patches. The PI will supervise all the participants closely and provide a weekly call to identify any issues. Participants will be monitored for any changes in baseline health. Participants will undergo blood work to determine serum T-level as well as their Prostate-specific antigen (PSA). There is no specific normal or abnormal level of PSA; however, a value above 1.4 ng/ml or increase of the PSA above 1.4 compared to baseline values will result in immediate cessation of TRT. We will also check the HCT every 4 weeks to ensure that hematocrit (HCT) is less than 54%, value greater than 54 may result in polycythemia.

Moreover, a staff physician who is board certified in SCI medicine will evaluate all participants who enroll in the study. This physician is competent to assess for urologic irritative or obstructive voiding symptoms and for changes in erectile function. This is a routine component of SCI medicine practice for patients with urologic symptoms related to both neurogenic voiding dysfunction and prostate hypertrophy. The physician will assess each participant for new symptoms every three months.

Study removal criteria may include:

- Extensive skin irritation or rashes or itching as result of TRT applications
- Medical history of carcinoma of the breast, carcinoma of the prostate, venous thromboembolism, pulmonary embolism, stroke, cholestatic jaundice, hypertension, serious heart problems, heart failure, myocardial infarction, ventricular arrhythmia, exertional chest pain, insulin dependent diabetes, hypercholesterolemia, hypertriglyceridemia, impaired liver function, or significant renal dysfunction.
- cardiovascular events similar to acute myocardial infarction, acute coronary syndrome, congestive heart failure, any cardiovascular-related hospitalization, stroke, or cardiac arrest, and the development of new significant ischemic findings or symptoms during the course of

the study (including development of new major abnormalities on serial EKGs or symptoms of typical angina)

- Serum PSA >4.0ng/ml
- Increase in serum PSA of >1.4ng/ml compared to baseline
- HCT >54%
- Liver enzymes (AST / ALT) >1.5 times normal upper limit
- Hemoglobin >17.5 g/dL
- Serum calcium between 10.5 11.2mg/dL with symptoms of hypercalcemia
- Gynecomastia
- Development of severe peripheral edema, as classified as 2+ or higher
- Development of any other SAE that the Medical Director, [name], feels necessitates study withdrawal for participant safety

Protection against possible subjects' coercion.

The \$3000 dollar amount dedicated as a reimbursement fee may create subject coercion. This amount reflects the cost of gas, transportation and commitment throughout the 1-year period. To protect against any coercion, the figure will be split into 6 payments (\$500 every two months or 16 visits). This means that each participant will receive ~ \$31.25 per study visit. The \$3000 figure will be re-calculated incase participants decide to lodge at Candlewood suites or perform the study at home using our established telehealth system. Finally, all our study procedures will be approved by the IRB and the PI will work closely with the IRB to avoid any coercive influence on any of our study participants.

c. Adverse Events

Participants will be monitored for any changes in baseline health. Their SCI provider will be notified if this occurs. An adverse event is any experience that has taken place during the course of research project, which, in the opinion of the investigators, was harmful to a subject participating in the research, increases the risks of harm in the research, or had an unfavorable impact on the risk/benefit ratio. Adverse events (AE) will be monitored throughout the study via exams, vital signs, laboratory tests, review of medical charts, and verbal concerns voiced by the participant or an associated friend or family member. Any adverse event will be documented in their files. Files will be reviewed for adverse events, protocol violations, and reasons for dropouts/withdrawals every ten days. The PI will provide the McGuire VA IRB & Office of Research Subjects Protections with an annual summary of adverse events. All serious adverse events (SAEs), such as those that are life-threating or involve hospitalization, s will be promptly reported to the McGuire IRB Research Subjects Protection Program. Participants' health conditions will be monitored during study visits.

When study procedures begin, the importance of reporting any perceived problem, adverse event or change from baseline health will be stressed to the subjects. Examples will be given to the subject of potential problems requiring immediate medical attention and potential problems requiring a phone call to the investigator. Above all, it will be stressed to the subject that direct phone access to the study staff is available 24hrs/day and if there is ever any doubt or concern on the part of the subject a call should be made. At the completion of this study all subjects will continue to receive their health care from their assigned SCI provider or other provider of subjects' own choice.

All subjects will be identified by an assigned number and their initials. Subjects' research charts will be kept inside a locked file in the PI's locked office. Only study staff listed on the Personnel List will have access to subject study records and medical information. A master sheet of

participants' full names will be kept in a locked file in the PI's office. All completed study files will be stored in the PI's SCI research office 1V-129. At the end of the 4 year period, all records will either be stored in the SCI Research Exercise Laboratory, which is a locked room or sent to Dunmar Storage Facility per direction of McGuire IRB.

8. Subjects' burdens

The current study was designed to reduce and minimize subject burden including transportation and participation time. Although participation may impose a significant burden, every effort will be taken by the study team to reduce the stressors and burdens of participation. Over the 1 year period, persons will be asked to visit the lab 4 times (1 visit for screening and consenting and 3 testing sessions for conducting outlined procedures) for testing. All exercise training will be conducted twice weekly over 1 year. Each training session should not last more than 30 minutes. The current study design will allow each participant to serve as his own control over all the genomic, dietary, body composition, metabolic and SCI factors that are likely to impact the outcomes of any training study. Every effort will be taken to retain participants in the study for 1 year. We have significant experience retaining participants up to 9 months that adhered to the applicant's CDA-2 study protocol. In the applicant CDA-2, the study constituted of 3 phases; a delay entry approach phase for 4 weeks, 16 weeks training phase and 16 weeks detraining phase. Out of the 26 participants who completed the first 2 phases, the applicant was successful in retaining 13 participants for the 3 phases (50%). The CDA2 study was designed to examine only 50% of the participants in the detraining phase (i.e. 6 participants/ group). Moreover. each participant is allowed to miss up to 10% (12 visits) of the scheduled visits without withdrawing from the study to consider unanticipated events similar to sickness, medical appointments and vacations. We believe that we can retain participants for up to one year using similar strategies.

- a) Previously we provided transportation using our facility owned Van (free of charge) to allow transportation to and from the VA facility.
- b) We have allowed operation and training beyond regular business hours to accommodate education and work related schedules.
- c) Total time commitment is less than 2 hours/ week, twice a week. Compared to other longitudinal clinical trials this is considered by far the least training volume, which was adopted according to the American College of Sports Medicine guidelines.
- d) During data collection, we will provide sufficient time for participants to have their meals and use medications.
- e) Trained research staff will help in the process of testing and data collection.
- f) The SCI Exercise Physiology Laboratory is equipped with a sound system and is in the process of installing a flat screen TV that will allow participants to listen to music or watch TV during exercise providing an interactive and motivational environment.
- g) A comprehensive team approach will be adopted that will allow participants to engage in recreational activity programs and to consult with a psychologist, dietitian or other clinical staff (PT, OT, etc.) as needed.

a. Benefits and Burdens

Potential benefits of research to subjects and others:

The risks associated with this study seem appropriate for the anticipated benefits. Study information will be under continuous review for any information that may impact on the risk/benefit ratio; i.e. adverse events, unanticipated problems, and complaints regarding the research. SCI persons with LMN denervation exhibit greater loss in muscle mass. The significant loss in muscle mass has been linked to several metabolic and cardiovascular health

related consequences. Individuals with SCI are at increased risk for many chronic diseases such as type II diabetes mellitus, dyslipidemia, cardiovascular disease and osteoporosis; it is important to continue developing exercise interventions that benefit these individuals and thereby decrease their risk for chronic disease. This understudied population represents 25% of the whole SCI population and cannot benefit from the standard applications of surface NMES on restoring muscle size similar to persons with SCI with intact LMN system. Results from the current investigation will facilitate a greater understanding of the methodology necessary to accurately determine the impact of long-term exercise on muscle hypertrophy, metabolic and local cellular adaptations. SCI predisposes individuals with denervated muscle to extreme muscle atrophy, decreased BMR, glucose intolerance and insulin resistance. Exercise has the potential to improve BMR, glucose effectiveness and insulin sensitivity in this population. Moreover, the benefits of long-term rehabilitation interventions are limited in individuals with lower motor neuron (LMN) denervation following SCI. The current proposal may provide a simple rehabilitation intervention to help restore muscle size and prevent heath related consequences. We hope findings from this application will help reduce the costs associated with managing secondary health related complications in Veterans and Civilians with SCI. The research team will extend every effort to disseminate the knowledge gained from this trial at various scientific meetings and journals to share nationally and internationally with other academics/clinicians. While there may be no direct benefit to the subjects besides the monetary reimbursement, the information learned in this study has the potential to help others in the future.

b. Importance of knowledge to be gained: The prevalence of individuals with SCI has been estimated to be 250,000-400,000 with an estimated 14% growth in the prevalence since 1988. Of the more than 46,000 Veterans with SCI-related disability, more than 60% are overweight or obese, more than 50% are glucose intolerant and 20% are frankly diabetic. In the last two decades, the national aggregate direct costs of SCI in the United States have increased with a concomitant decline in mortality over the first year after SCI.⁶ Our preliminary data suggested that 20-25% experience SCI with LMN denervation. Currently, there is no available rehabilitation intervention following lower motor neuron (LMN) denervation. Denervation to lower extremity muscles results in even more deleterious sub-lesional skeletal muscle atrophy and is accompanied with several SCI health-related consequences. The current proposal will provide a novel rehabilitation strategy, combining both TRT+LPWS to determine the effects of mitigating muscle loss following LMN denervation. Establishing the LPWS rehabilitation protocol is a rigorous process and may require several attempts to refine and establish the best stimulation protocol necessary for stimulation of LMN denervation. The addition of TRT may provide additional benefits of increasing lean mass and accelerate the actions of LPWS. Previous attempts indicate that TRT may increase lean mass and BMR. This will be the first clinical attempt to determine the role of TRT on muscle size and lean mass in persons with LMN denervation independent of neural structures. This is a promising combination of physical and pharmacologic therapy that is likely to improve body composition and other cellular functions which may improve other metabolic health biomarkers. Several of the mechanisms involved in increasing muscle size, including proteins and gene expression will be studied, which will allow us to design specific interventions that target specific abnormalities at the cellular level which have the potential to impact body composition and metabolic adaptations in future studies.

9. Clinical Trials Requirements. This is a drug trial and registration with Clinical Trials is mandated. We are aware of this requirement and are experienced in complying with all regulatory requirements. The PI has previous experience working with Clinical Trials and he successfully registered two clinical trials.

10. Data Safety and Monitoring Board (DSMB):

